Patients who prematurely discontinue the study should return and complete assessments associated with the Week 24 visit (4 weeks after the last study treatment, see [Table 6-1](#)) and any AEs that are treatment emergent should be reported until 12 weeks after the last study treatment. The final visit should be performed before any new treatment is initiated.

Patients who prematurely withdraw from the study will not be replaced.

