Chest X-ray or MRI (for study eligibility)	X											X	A chest X-ray or MRI is required if it was not performed and evaluated within 3 months before Screening. The X-ray should be performed after it is certain the patient meets inclusion/exclusion criteria in order to minimize unnecessary exposure to radiation. In some sites selected, the X-ray may be replaced by a chest MRI assessment.
Electrocardiogram	X											X	
Hematology	X	X					X	X	X		X	X	

	Screening	Treatment Period 1 Double-blind placebo-controlled (last dose at Week 4)					Treatment Period 2 Double-blind active (last dose at Week 20)					USV**	Comments
		1	2	3	4	5	6	7	8	9	10 EOS/ PPD*		
Visit number	1	2	3	4	5	6	7	8	9	10 EOS/ PPD*			* EOS/PPD - Patients who prematurely discontinue during the treatment period should return for assessments associated with the Week 24 visit (i.e. 4 weeks after the last study treatment). ** Unscheduled visit – assessments at the discretion of the investigator.
Week	-10 to -1	0	1	2	3	4	8	12	20	24			
Recommended visit window (days)			± 2	± 5	± 5	± 5							
Blood chemistry	X	X				X	X	X		X	X		Blood sample to be collected with patient in fasting state.
HLA-B27	X												
High sensitivity C-reactive protein	X	X					X			X	X		Results should be blinded in the laboratory report after Visit 2.
Urinalysis	X	X				X	X	X		X	X		Urine dipstick test to be performed at site. Test supply will be provided by central laboratory.
Serum pregnancy test	X										X		
Urine pregnancy test		X				X	X	X		X	X		Test to be performed at site. Test supply will be provided by central laboratory.
Hepatitis B, C or HIV serology (only in countries where required)	S												Hepatitis B and/or hepatitis C and/or HIV serology testing to be performed during Screening period only if required as per local medical practice or local regulations prior to initiation of therapy.

	Screening	Treatment Period 1 Double-blind placebo-controlled (last dose at Week 4)					Treatment Period 2 Double-blind active (last dose at Week 20)				USV**	Comments
		1	2	3	4	5	6	7	8	9		

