Visit number	1	2	3	4	5	6	7	8	9	10 EOS/ PPD*		* EOS/PPD - Patients who prematurely discontinue during the treatment period should return for assessments associated with the Week 24 visit (i.e. 4 weeks after the last study treatment). ** Unscheduled visit – assessments at the discretion of the investigator.
Week	-10 to -1	0	1	2	3	4	8	12	20	24		
Recommended visit window (days)			± 2	± 5	± 5	± 5						
												These assessments will be documented in source records only and will not be entered into the eCRF.
Randomization via IRT		X					X †					† At Visit 8, non-responders and patients receiving placebo will be re-randomized to secukinumab 150 mg or 300 mg
IRT contact such as for registration or drug supply including home administration	X	X	X	X	X	X	X	X	X	X		
Administration of study treatment		X	X	X	X	X	X	X	X			Patients will be required to self-administer secukinumab at home at Week 16. Please refer to Table 6-2 for timing of home administration.
Check self-administration log for home administration									S			At Visit 9, patients must return the self-administration log along with all dispensed PFS and drug packaging

	Screening	Treatment Period 1 Double-blind placebo-controlled (last dose at Week 4)					Treatment Period 2 Double-blind active (last dose at Week 20)				USV**	Comments
		1	2	3	4	5	6	7	8	9		
Visit number	1	2	3	4	5	6	7	8	9	10 EOS/ PPD*		* EOS/PPD - Patients who prematurely discontinue during the treatment period should return for assessments associated with the Week 24 visit (i.e. 4 weeks after the last study treatment). ** Unscheduled visit – assessments at the discretion of the investigator.
Week	-10 to -1	0	1	2	3	4	8	12	20	24		
Recommended visit window (days)			± 2	± 5	± 5	± 5						
Spinal pain assessment on NRS	X	X	X	X	X	X	X	X	X	X	X	
BASDAI	X	X	X	X	X	X	X	X	X	X	X	
PASS		X	X	X	X	X	X	X	X	X	X	
Patient global assessment of disease activity		X					X			X	X	
FACIT-Fatigue®		X					X			X	X	
ASAS Health Index		X					X			X	X	
Treatment completion form										X		

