2.1.2 Visits windows

Visit windows will be used for the data that is summarized by visit; they are based on the study evaluation schedule and comprise a set of days around the nominal visit day. For any assessment, there are the protocol defined scheduled visits around which visit windows are created in SAP to cover the complete range of days within the study. The visit windows are shown in [Table 2-1](#). These apply to measurements taken at every visit. For assessments collected less often, different visit windows will be applied as detailed below.

When visit windows are used, all visits will be re-aligned, i.e., they will be mapped into one of the visit windows. E.g., if the *Week 4* visit of a subject is delayed and occurs on Day 46 instead of on Day 29, say, it will be re-aligned to visit window *Week 8*. In the case of major deviations from the visit schedule, or due to unscheduled visits, several assessments of a subject may fall in a particular visit window (either scheduled or unscheduled). Statistical approaches to handle multiple assessments in a given visit window are specified below.

Of note, subjects are allowed to have gaps in visits.

Table 2-1 Assessment windows for scheduled visits

Analysis Visit	Week	Scheduled Day	Visit Window
Baseline	BSL	1*	
Week 1	1	8	Day 2-11
Week 2	2	15	Day 12-18
Week 3	3	22	Day 19-25
Week 4	4	29	Day 26-43
Week 8	8	57	Day 44-71**
Week 12	12	85	Day 72-113
Week 20	20	141	Day 114-151
Week 24	24	162	>=152 Days

* Baseline measurement before the first drug administration for safety assessments and before the randomization for efficacy assessments. For efficacy visit windows, refer to date of randomization.

** For primary endpoint analysis, data will be considered as Week 8 data, if Week 8 dose administration was done on or after the assessment date.

For parameters, which are not collected at every visit (e.g., FACIT-Fatigue[©], ASAS Health Index), visit windows defined in [Table 2-1](#) will be combined. For example, if a parameter is measured at Week 12 and Week 24 only, Week 12 visit window will extend from Day 2 to Day 113 (combining Week 1 to Week 12 visit windows), Week 24 will extend from Day 114 to >=152 days (combining Week 20 to Week 24). If more than one assessment falls into the interval, the rules defined in [Section 2.1.3](#) below are applied.

Table 2-2a Assessment windows for scheduled visits of Exposure Data

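### For items scheduled only at Weeks 8 and 24, the combined visit windows label early-exit values as Week 8 or Week 24, and the pre-dose condition on Week 8 data covers only the primary endpoint

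*SAP*

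**What the plan says.** SAP 2.1.2 sets a separate rule "For parameters, which are not collected at every visit", naming FACIT-Fatigue and the ASAS Health Index as examples. Adjacent Table 2-1 windows are merged. In the worked example, a parameter measured at Weeks 12 and 24 only, the "Week 12 visit window will extend from Day 2 to Day 113" and "Week 24 will extend from Day 114 to >=152 days". If several values fall in one window, SAP 2.1.3 takes the closest for quantitative variables, and the earlier one in a tie.

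A footnote to Table 2-1 accepts a value as Week 8 data only if the Week 8 dose was given on or after the assessment date. It is worded for the primary endpoint analysis alone. SAP 2.1.1 nevertheless places all Week 8 assessments in Treatment Period 1 and the Week 8 dose in Treatment Period 2.

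In Protocol Table 6-1, the row "ASAS Health Index" and the FACIT-Fatigue row are marked after baseline only at Week 8, Week 24 and unscheduled visits. The rows "Patient global assessment of disease activity" and "High sensitivity C-reactive protein", both ASDAS components, have the same post-baseline schedule. Spinal pain NRS and BASDAI are collected at every visit.

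Under Protocol 5.6.2, patients who leave early should return and "complete assessments associated with the Week 24 visit (4 weeks after the last study treatment"; Table 6-1 repeats this timing. Protocol section 6 instead asks for the final visit as soon as possible.

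**The concern.** A by-visit table is read as showing the effect of a given time on treatment. If the Week 8 window opens on Day 2 and the Week 24 window on Day 72, a value taken after a fraction of a period's dosing can stand as the result for the whole period. The exit visit supplies exactly such values. The tie-break seldom removes them, because the exit value is usually the only one in its window.

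The second gap concerns the Week 8 switch, when placebo patients start active drug. A post-dose value labelled Week 8 would enter the Group A versus Group B comparison although it belongs to Period 2. The SAP guards against this for spinal pain response but for no other Week 8 efficacy endpoint.

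At stake are the Week 8 comparisons of A with B and the Week 24 comparisons of A2 with A3 and B1 with B2 that SAP Table 1.2-1 lists for FACIT-Fatigue and ASDAS, together with the ASAS Health Index summaries by arm.

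**Working it through.** **Inputs.** Table 2-1 windows: Week 1 = Day 2-11, Week 2 = 12-18, Week 3 = 19-25, Week 4 = 26-43, Week 8 = 44-71, Week 12 = 72-113, Week 20 = 114-151, Week 24 = 152 onward. Dosing from SAP 1.1: Weeks 0, 1, 2, 3 and 4, then Weeks 8, 12, 16 and 20. Dose day = 7 x week + 1, which gives Days 1, 8, 15, 22 and 29, then 57, 85, 113 and 141. Randomization and first dose are taken to fall on the same day.

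**Rule.** Each scheduled visit takes every day after the previous scheduled visit's window (from Day 2 for the first), up to the end of its own window.

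**Check against the SAP example.** For Weeks 12 and 24 this gives Day 2-113 and Day 114 onward, as printed.

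**Applied to Weeks 8 and 24.** Week 8 = Day 2-71 and Week 24 = Day 72 onward. These limits are not printed; they follow from the rule and Table 6-1.

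**Exit values.** Exit day = last dose day + 28.

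| Last dose received | Exit day | Label for FACIT-Fatigue, ASAS HI | Label for NRS, BASDAI |
|---|---|---|---|
| 1st in Period 1 (Day 1) | 29 | Week 8 | Week 4 |
| 2nd in Period 1 (Day 8) | 36 | Week 8 | Week 4 |
| 3rd in Period 1 (Day 15) | 43 | Week 8 | Week 4 |
| 4th in Period 1 (Day 22) | 50 | Week 8 | Week 8 |
| 5th in Period 1 (Day 29) | 57 | Week 8 | Week 8 |
| 1st in Period 2 (Day 57) | 85 | Week 24 | Week 12 |
| 2nd in Period 2 (Day 85) | 113 | Week 24 | Week 12 |
| 3rd in Period 2 (Day 113) | 141 | Week 24 | Week 20 |
| 4th in Period 2 (Day 141) | 169 | Week 24 | Week 24 |

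Six of the nine rows give one visit two labels. The two protocol statements on exit-visit timing need reconciling, but the result does not depend on which applies: an earlier exit visit only moves the value further from Week 8 or Week 24.

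**ASDAS.** The combining rule does not name it. Its BASDAI items are collected at every visit and so use Table 2-1; patient global and hsCRP fall under the combined windows. At a Day 29 exit, the BASDAI items belong to Week 4 and the other two components to Week 8. The SAP does not say whether ASDAS is windowed as a composite or by component.

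**Post-dose values.** With the Week 8 dose on Day 57, Days 58-71 lie after the switch but inside the Week 8 window, combined or not. Outside the primary endpoint, only the closest-value rule protects the comparison. It fails if the pre-dose value is missing. It can also fail if the visit was early: with assessment and dose on Day 55 (allowed by the 2-day visit window), an unscheduled value on Day 58 is 1 day from the scheduled Day 57, against 2 for the pre-dose value. This gap includes BASDAI response, the secondary endpoint.

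**The case against.** The convention is disclosed. The SAP states the rule, gives an example, and says the windows are meant to cover the whole range of study days. A reader might call it an undeclared carry-forward; the documents do not support that. What stands is that the example does not show what the rule does on a Week 8 and Week 24 schedule.

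Post-dose Week 8 values should be rare. Protocol 5.5.4 requires assessments to be completed before injection, and no visit is scheduled between Weeks 8 and 12. It takes an unscheduled visit or an immediate exit visit, together with a missing or more distant pre-dose value. This is a wording gap of small practical reach.

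Two stronger readings are tempting. One is that exit values arise as early as Day 10 for Week 8 or Day 75 for Week 24. Those days rest only on the as-soon-as-possible instruction in Protocol section 6; on the four-week timing the earliest are Day 29 and Day 85. The other is that a Week 24 value may follow only one or two doses in all. For A2 and A3, the first Period 2 dose comes after five scheduled Period 1 doses.

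Narrower windows also have a price. They drop early leavers' data from FACIT-Fatigue, for which the SAP states no missing-data method. That objection stands, and the fix has to say so.

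**Conclusion.** The point holds as a low-cost clarification. Followed as written, the combining rule mislabels time on treatment for FACIT-Fatigue and the ASAS Health Index, and by inference for the patient global and hsCRP components of ASDAS. The pre-dose condition is narrower than the SAP's own definition of Treatment Period 1.

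The primary endpoint is unaffected: spinal pain keeps Day 44-71 and has the pre-dose condition. BASDAI response also keeps Day 44-71 and is exposed only to the rare post-dose value. The combined windows themselves affect exploratory endpoints only.

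The number of affected patients cannot be computed. A reader might take the step from 332 to 352 patients (20/352 = 5.7%) as a drop-out rate and infer about 20 mislabelled Week 24 values, or a handful per re-randomized arm. The documents do not support that. The allowance belongs to the Week 8 sample size, also covers protocol deviations, and is not a Period 2 exit rate. Patients who leave before the Week 8 dose are not in FAS-TP2, and not everyone who leaves attends an exit visit.

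The conclusion assumes that the combining rule is applied to the Week 8 and Week 24 schedule as in the SAP's example, and that exit visits take place as the protocol asks.

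**What to change.** Amend SAP 2.1.2, with matching lines in 2.11 and 2.13:

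1. Apply the condition that the assessment falls on or before the Week 8 dose date to all Week 8 efficacy data.
2. For items scheduled after baseline only at Weeks 8 and 24, use the Table 2-1 windows (Day 44-71 and Day 152 onward) in place of combined windows. List values outside them. State that ASDAS is windowed as one composite by visit.
3. For ASDAS and ASAS Health Index responses, count a missing value as non-response, as SAP 2.5.3 and 2.7.3 already do for spinal pain and BASDAI at Week 8. Name this as an addition, since the SAP states no such rule for these endpoints, and say that it also applies at Week 24.

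The cost is SAP text and programming; no new data are needed. The downside is that early-exit values leave the by-visit tables. FACIT-Fatigue and ASAS Health Index score summaries then become observed-case and may be selective if early leavers differ from those who stay. The report should describe them as such.

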2.1.3 Multiple assessments within visit windows

When there are *multiple assessments* in a particular visit window, the following rules are applied to select one value “representing” the subject in summary statistics in a visit window (see [Table 2-1](#)).

For baseline assessment definition, see [Section 2.1.1](#). For post-baseline visit windows, the following applies (unless otherwise specified):

- for *quantitative variables*, the *closest* to the actual visit is chosen (if two assessments have the same distance, then the earlier one will be chosen);
- for *qualitative variables*, the *worst* record is selected. It is noted that in the analyses performed, *worst* case is always well defined.
- in case qualitative variables are based on quantitative variables, e.g. spinal pain NRS response, the visit will be assigned to the quantitative variable, and this visit will be used for the derived qualitative variable.

Table 2-3 Rules for selecting values for analysis

Timing of measurement	Type of data	Rule
Baseline	All data	See Section 2.1 Data analysis general information
Post-baseline efficacy	All data	Cases where the same parameter is recorded more than once on the same date will be handled as follows: 
• If time of completion exists the earliest measurement will be used;• If time does not exist the measurement from the lowest CRF visit number will be used.

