**Table 6-1 Assessment schedule**

	Screening	Treatment Period 1 Double-blind placebo-controlled (last dose at Week 4)					Treatment Period 2 Double-blind active (last dose at Week 20)				USV**	Comments
Visit number	1	2	3	4	5	6	7	8	9	10 EOS/ PPD*		* EOS/PPD - Patients who prematurely discontinue during the treatment period should return for assessments associated with the Week 24 visit (i.e. 4 weeks after the last study treatment). ** Unscheduled visit – assessments at the discretion of the investigator.
Week	-10 to -1	0	1	2	3	4	8	12	20	24		
Recommended visit window (days)			± 2	± 2	± 2	± 2	± 2	± 5	± 5	± 5		
Information and informed consent	X											
Inclusion & exclusion criteria	X	X										
axSpA history		X										
Spinal pain responder assessment							X					
Demographics	X											
Relevant medical history/ current medical conditions	X											
Prior medication/ concomitant medication	X	X	X	X	X	X	X	X	X	X	X	
AEs/ SAEs (including injection site reactions)	X	X	X	X	X	X	X	X	X	X	X	AEs/SAEs occurring after the patient has signed the informed consent (including those that occur during home administration of study drug) must be captured on the appropriate eCRF page. Any AEs that are treatment-emergent should be reported until 12 weeks after the last study treatment.

	Screening	Treatment Period 1 Double-blind placebo-controlled (last dose at Week 4)					Treatment Period 2 Double-blind active (last dose at Week 20)					USV**	Comments
		1	2	3	4	5	6	7	8	9	10 EOS/ PPD*		
Visit number	1	2	3	4	5	6	7	8	9	10 EOS/ PPD*			* EOS/PPD - Patients who prematurely discontinue during the treatment period should return for assessments associated with the Week 24 visit (i.e. 4 weeks after the last study treatment). ** Unscheduled visit – assessments at the discretion of the investigator.
Week	-10 to -1	0	1	2	3	4	8	12	20	24			
Recommended visit window (days)			± 2	± 5	± 5	± 5							
Smoking history		X											
Cardiovascular medical history	X												
Physical examination	S	S	S	S	S	S	S	S	S	S	S		
Height† and weight		X								X	X		† Height will be assessed at Visit 2 or unscheduled visit only.
Vital signs	X	X	X	X	X	X	X	X	X	X	X		
QuantIFERON TB-Gold test	X											X	

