#### 6.4.5 Patient acceptable symptoms state

The PASS has been defined as the highest level of symptoms beyond which patients consider themselves well. Measurement of patient well-being also enables evaluation of how soon and for how long the patient feels good (Maksymovych et al, 2010).

During the PASS assessment, the patient will answer the following question:

- Considering all the different ways your disease is affecting you, if you would stay in this state for the next months, do you consider that your current state is satisfactory?

The purpose of PASS in this study is to assess the well-being of patients with axSpA. Achievement of PASS indicates that the patient feels well.

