Proportion of patients achieving a satisfactory Patient Acceptable Symptom State (PASS) at Week 1, 2, 3, 4 and 8 with secukinumab 150 mg compared to placebo.	Proportion of patients achieving a satisfactory PASS at Week 1, 2, 3, 4 and 8 in Group A compared to Group B.

Proportion of patients in each of treatment arm achieving a satisfactory PASS at Week 12, Week 20 and Week 24.	Proportion of patients achieving a satisfactory PASS at Week 12, Week 20 and Week 24 in Arm A1, Arm A2 vs Arm A3, and Arm B1 vs Arm B2.
Spinal pain NRS score according to previous exposure to tumor necrosis factor (TNF) inhibitors at Week 1, 2, 3, 4, 8, 12 and 24	Proportion of patients achieving a spinal pain score < 4 for TNF-naïve patients compared to TNF α -IR patients at Week 1, 2,3, 4, 8, 12 and Week 24
Proportion of patients who responded to secukinumab 150 mg at Week 8 (i.e. spinal pain score < 4 on a 0-10 NRS) maintaining a response at Week 24.	Proportion of patients with spinal pain score < 4 on a 0-10 NRS at Week 8 maintaining a spinal pain score < 4 at Week 24.
Proportion of patients achieving an improvement in ASAS health index with secukinumab 150 mg compared to placebo at Week 8.	Proportion of patients achieving an improvement in ASAS health index with secukinumab 150 mg compared to placebo at Week 8.
Proportion of patients achieving an improvement in ASAS health index in each treatment arm at Week 24.	Proportion of patients achieving an improvement in ASAS health index in each treatment arm at Week 24.
ASAS health index at Week 8 and Week 24.	Mean ASAS health index score in each treatment arm at Week 8 and Week 24
Change from baseline in total spinal pain NRS score at all time points.	Total spinal pain NRS score in each treatment arm at all time points.
Change from baseline in total BASDAI score at all time points.	Total BASDAI score in each treatment arm at all time points.
ASDAS-CRP at Week 8 and Week 24.	Mean ASDAS-CRP in each treatment arm at Week 8 and Week 24.
[REDACTED]	
[REDACTED]	
Safety and tolerability of secukinumab 150 mg and 300 mg over the study period.	Safety and tolerability, as measured by frequency and severity of adverse events and changes in laboratory values of interest for secukinumab 150 mg and placebo (Baseline to Week 8) and for secukinumab 150 mg and 300 mg (Week 8 to Week 24).

2 Statistical methods

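### SAP 2.1.3 scores PASS from the worst answer in a visit window, so extra visits can only lower the PASS rate; the effect on the arm difference is small and of unknown sign

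*SAP*

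**What the plan says.** SAP 2.1.3 has three rules for post-baseline windows that hold more than one assessment:

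- Scores: "for *quantitative variables*, the *closest* to the actual visit is chosen", with the earlier record taken if two are equally distant.
- Categories: "for *qualitative variables*, the *worst* record is selected".
- Categories derived from a score, with spinal pain response as the example: "the visit will be assigned to the quantitative variable, and this visit will be used for the derived qualitative variable".

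Table 2-3 in the same section deals only with repeats on one date: "If time of completion exists the earliest measurement will be used".

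PASS is asked directly (Protocol 6.4.5): "do you consider that your current state is satisfactory". It has no underlying score, and SAP 2.11 sets no selection rule for it. SAP Table 1.2-1 lists as an exploratory endpoint: "Proportion of patients achieving a satisfactory PASS at Week 1, 2, 3, 4 and 8 in Group A compared to Group B". A further PASS endpoint covers Weeks 12, 20 and 24 by arm.

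SAP 2.1.2 expects more than one assessment in a window after major schedule deviations or unscheduled visits. Its own example is that "if the *Week 4* visit of a subject is delayed and occurs on Day 46 instead of on Day 29, say, it will be re-aligned"; the destination is the Week 8 window. Protocol Table 6-1 marks PASS in the unscheduled-visit column, with the note: "Unscheduled visit – assessments at the discretion of the investigator".

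**The concern.** A worst-of-several rule suits safety categories, where the aim is to miss nothing. Applied to an efficacy responder rate, it gives a patient with two answers two chances to be scored unsatisfactory, while a patient with one answer has one chance. The reported rate then partly reflects how often patients were seen.

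In the SAP's own Day 46 example, Week 8 PASS becomes the worse of a delayed Week 4 answer and the Week 8 answer. The Week 8 pain response of the same patient comes from the closest record. PASS and pain response labelled with the same week can thus come from different dates. The SAP already protects pain response from this rule and leaves PASS out.

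At stake is the descriptive PASS profile by week and arm, and the exploratory comparison of Groups A and B up to Week 8.

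**Working it through.** **Which endpoints are reached.** The spinal pain, BASDAI and ASDAS responses are cut-offs on a score, so the derived-variable rule covers them. PASS is not. Table 2-3 does not help when the two answers are on different days.

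**How a second answer gets into a window.** From SAP Table 2-1, the lateness needed to leave a window is its last day + 1 − the scheduled day:

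- Weeks 1, 2 and 3: 12−8, 19−15 and 26−22 = 4 days
- Week 4: 44−29 = 15 days
- Week 8: 72−57 = 15 days
- Week 12: 114−85 = 29 days
- Week 20: 152−141 = 11 days

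Protocol Table 6-1 recommends ±2 days up to Week 8 and ±5 days after, so visits kept to schedule do not collide with one another. The windows are contiguous, however, so any post-baseline unscheduled PASS answer falls into one of them. The final-visit assessments of early discontinuers (Protocol 6), which include PASS, can also share a window with a scheduled visit.

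**Week 8.** The footnote to Table 2-1 that limits Week 8 data to assessments no later than the Week 8 dose is written for the primary endpoint. For PASS, an answer up to Day 71, after re-randomization to active treatment, can count as Week 8.

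**Size.** The documents give no PASS rate, extra-visit rate or agreement between answers, so there is no figure in the plan to reproduce. Everything below is an assumption. Let p be the chance of a satisfactory answer, κ the agreement between two answers in one window, and q the share of patients with a second record.

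- P(both satisfactory) = p² + κp(1−p)
- Loss per patient with two records = (1−κ)p(1−p)
- Loss in the arm = q(1−κ)p(1−p)

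| | κ = 0.3 | κ = 0.5 | κ = 0.7 |
|---|---|---|---|
| Secukinumab, p = 0.50: P(both) | 0.325 | 0.375 | 0.425 |
| Loss per affected patient (points) | 17.5 | 12.5 | 7.5 |
| Arm loss, q = 5% (points) | 0.875 | 0.625 | 0.375 |
| Placebo, p = 0.30: P(both) | 0.153 | 0.195 | 0.237 |
| Loss per affected patient (points) | 14.7 | 10.5 | 6.3 |
| Arm loss, q = 10% (points) | 1.47 | 1.05 | 0.63 |
| Change in the 20-point difference | +0.595 | +0.425 | +0.255 |

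**Sign.** Only q needs to change to reverse it.

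- Swapped (secukinumab 10%, placebo 5%): losses of 0.75 to 1.75 and 0.315 to 0.735, so the difference narrows by about 0.4 to 1.0 points.
- Equal at 10%: losses of 0.75 to 1.75 and 0.63 to 1.47, so it narrows by about 0.1 to 0.3 points.
- Break-even: placebo needs 0.25/0.21 = 1.19 times the secukinumab share of extra records before the difference widens.

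**Second check.** This borrows the planning rates for NRS response (43.6% and 23.5%, Protocol 9.8) as stand-ins for PASS. Let d be the chance that the second answer is unsatisfactory when the scheduled one is satisfactory. The arm loss is p·q·d.

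- With q from 5% to 20% and d from 0.1 to 0.5, the loss runs from 0.235×0.05×0.1 = 0.1 points to 0.436×0.20×0.5 = 4.4 points.
- With d = 0.3, the 20.1-point difference becomes 19.5 (q = 10% in both arms), 20.5 (5% secukinumab, 15% placebo) or 18.5 (15% secukinumab, 5% placebo).
- With equal d, break-even is 0.436/0.235 = 1.86.

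**The case against.** The strongest reply has four parts.

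**Direction.** A reader might infer that placebo patients make more unscheduled visits, so their PASS rate is pushed down further and the treatment difference is inflated. The documents do not support this. Nothing in them gives extra-visit rates by arm. If adverse events prompt such visits, Protocol 3.7 reports a higher total rate on secukinumab than on placebo in earlier trials, which points the other way. Nor does the arm with more extra visits always lose more points, as the break-even ratios show. This part stands.

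**Mechanism.** An extra record prevails only when it is worse, so a scheduled unsatisfactory answer is never changed. Late visits must be well outside the protocol windows to collide, and PASS at an unscheduled visit is discretionary. This stands and limits the frequency, but the unscheduled route remains.

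**Materiality.** PASS is exploratory. SAP 2.11 lists it as proportions by group, and it is absent from the SAP 2.13 list of categorical endpoints that receive confidence intervals and possibly p-values. This stands, although Table 1.2-1 does frame it as Group A compared with Group B.

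**Conservatism.** It may be said that a prespecified worst-case rule is simply cautious. It is cautious for each arm's rate, but not necessarily for the difference. This part does not stand.

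**Conclusion.** The point holds as a minor one. Followed as written, SAP 2.1.3 puts PASS under the worst-record rule, and no other section corrects this. Relative to the scheduled answer, the PASS rate can only stay equal or fall, and the fall grows with the number of patients who have a second record.

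With 10% of placebo and 5% of secukinumab patients having a second record, PASS rates of 30% and 50%, and κ of 0.3 to 0.7, the arms lose about 0.6 to 1.5 and 0.4 to 0.9 points and the difference moves by about 0.3 to 0.6 points. It widens in that example and narrows in others that are equally consistent with the documents, so the sign is unknown. The 6 to 17.5 point losses apply only to patients with two records and should not be read as an effect on an arm. The primary and secondary endpoints, the ASDAS responses and the sample size are not affected.

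**What to change.** In SAP 2.1.3, add a rule for PASS:

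- Use the answer from the visit that the protocol schedules for that week. If the window contains none, use the record closest to the nominal day, the earlier one if tied. Closest-to-day alone would not be enough: an unscheduled Day 57 answer would displace a scheduled Week 8 answer given on Day 59.
- Apply to Week 8 PASS the pre-dose restriction that Table 2-1 already states for the primary endpoint.
- Limit the worst-record rule to safety categories.

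The fallback relies on the nominal days. Check the Week 24 entry in Table 2-1, which is Day 162, whereas the other post-baseline rows follow 7 × week + 1, giving 169.

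The cost is a small change in derivation and no new data. The worst-record version can be kept as a sensitivity analysis, with the number of extra PASS answers reported by arm.
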